5.2.5.2 Secondary efficacy analyses

For all secondary efficacy endpoints, the analyses will be based on observed data only *i.e.*, no data will be imputed. All the following analyses will be performed on both the ATS and the PP analysis data set.

SO1: *To determine the effect size of PRM-151 relative to placebo in change from Baseline to Week 28 in normal lung parenchyma (normal + mild LAA) and interstitial lung abnormalities (ILA) as quantified on high-resolution CT (HRCT) imaging analysis, pooling subjects on a stable dose of pirfenidone or nintedanib with subjects not on other treatment for IPF.*

HRCT is performed at baseline and W28. Descriptive statistics will be computed by treatment group for baseline, week 28 and change from baseline to Week 28 in total lung volume and volume (in ml and % of total lung volume) of parenchyma features representative of normal lung (normal + mild LAA) and representative of interstitial lung abnormalities (ILA) as quantified by HRCT imaging (see section 8, Statistical table 14.2.6.1.1 and 14.2.6.2.2). A model similar to that of the primary analysis (see section 5.2.5.1) will be used to compare the two groups (Statistical tables 14.2.6.3.1 to 14.2.6.3.2, Figure 14.2.4.1 to 14.2.4.2). Individual's measurement of total lung volume and volume of parenchymal features quantified by HRCT imaging will be reported in Listing 16.2.6.3.

SO2: *To determine the effect size of PRM-151 relative to placebo in change from Baseline to Week 28 in mean FVC% predicted, separately in subjects on a stable dose of pirfenidone or nintedanib and in subjects not on other treatments for IPF.*

The same model as the one for the primary analysis (see section 5.2.5.1) will be used for each subgroup (Statistical table 14.2.7.1.1 to 14.2.7.2.2, Figure 14.2.5.1.1 to 14.2.5.2.2). All measurements of FVC [% predicted] will be reported in Listing 16.2.6.1.1.

SO3: *To determine the effect size of PRM-151 relative to placebo in change from Baseline to Week 28 in normal lung (defined as normal + mild LAA) parenchyma and interstitial lung abnormalities (ILA) as quantified on HRCT imaging analysis, separately in subjects on a stable dose of pirfenidone or nintedanib and in subjects not on other treatments for IPF.*

Descriptive statistics will be computed by treatment group and stratification level for week 0, week 28 and change from baseline to Week 28 in total lung volume and volume (in ml and % of total lung volume) of parenchyma features representative of normal (normal + mild LAA) lung and representative of interstitial lung abnormalities (ILA) as quantified by HRCT imaging (see section 8). A model similar to that of the primary analysis (see section 5.2.5.1) will be used to compare the two groups (Statistical table 14.2.8.1.1.1 to 14.2.8.2.3.2, Figure 14.2.6.1.1 to 14.2.6.2.2).

Individual's measurement of total lung volume and volumes of parenchymal features quantified by HRCT imaging will be reported in Listing 16.2.6.3.

SO4: To assess the tolerability and safety of PRM-151 in subjects with IPF through Week 28.

See Section 5.2.6 safety analysis.

SO5: To assess the ability of PRM-151 to reduce disease-related events associated with mortality

See Section 5.2.6 safety analysis.

SO6: To determine the effect size of PRM-151 relative to placebo on pulmonary function in addition to mean change in FVC% predicted

To determine the effect size of PRM-151 relative to placebo on pulmonary function, descriptive qualitative statistics and Odds-Ratios (PRM-151 /Placebo) with their 90% CIs will be calculated by treatment group and stratification level for:

- Subjects with a decline in FVC [% predicted] of $\geq 5\%$ and $\geq 10\%$ from baseline to week 28.
- Subjects with a decline in FVC [ml] of $\geq 100\text{ml}$ and $\geq 200\text{ml}$ from baseline to week 28.
- Subjects with an increase in FVC [% predicted] of $\geq 5\%$ and $\geq 10\%$ from baseline to week 28.
- Subjects with an increase in FVC [ml] of $\geq 100\text{ ml}$ and $\geq 200\text{ ml}$ from baseline to week 28.
- Subjects with stable disease by FVC [% predicted], defined as a change in FVC [% predicted] of $< 5\%$ from baseline to week 28.
- Subjects with stable disease by FVC in ml, defined as a change in FVC [ml] of $< 100\text{ml}$ from Baseline to week 28.

For each of these endpoints treatment groups will be compared using the Cochran-Mantel-Haenszel general association test available in the SAS Freq procedure, adjusting for the Stratum effect (Statistical table 14.2.9.1 to 14.2.9.2). Due to the small sample-size, the exact version of the test will be used. Odds ratio (with 90% CI) together with p-values will be reported.

SO7: To determine the effect size of PRM-151 relative to placebo on 6-minute walking distance

The same descriptive statistics and analysis model as those of the primary analysis (see section 5.2.5.1) will be used (Statistical tables 14.2.10.1.1 to 14.2.10.3.2, Figure 14.2.7.1 to 14.2.7.2). All results of the 6-minute walk test will be reported in Listing 16.2.6.2.

SO8: To determine the effect size of PRM-151 relative to placebo on DLCO.

The same descriptive statistics and analysis model as those of the primary analysis (see section 5.2.5.1) will be used (Statistical tables 14.2.11.1.1 to 14.2.11.3.2, Figure 14.2.8.1 to 14.2.8.2). All DLCO measurements will be reported in Listing 16.2.6.1.2.

SO9: To determine the correlation between change in FVC [% predicted] and total lung volume and volume of ILA on HRCT from Baseline to Week 28

Correlation between change from baseline in FVC[% predicted] and (i) total lung volume (Statistical table 14.2.12.1.1 and 14.2.12.1.2, Figures 14.2.9.1.1 and 14.2.9.1.2) and (ii) volume of ILA on HRCT will be produced along with the corresponding scatter plots (Statistical table 14.2.12.2.1 and 14.2.12.2.2, Figures 14.2.9.2.1 and 14.2.9.2.2).

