5.2. Withdrawal and Replacement of Subjects

The Investigator may withdraw a subject from the study for any of the following reasons:

- Subject, Investigator, or Sponsor request.
- Protocol violation.
- AE.
- Pregnancy (mandatory).
- Progression of disease that, in the opinion of the Investigator, precludes further study drug treatment.
- Subject decision. A subject may withdraw consent to participate in the study at any time.

The reason for study withdrawal is to be documented in the subject's source documents and electronic case report form (eCRF).

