3.1.3 Study treatment discontinuations - Study discontinuations

The Investigator may discontinue study drug treatment prematurely for any of the following reasons:

- Subject, Investigator, or Sponsor request
- Protocol violation
- AE
- Pregnancy
- Progression of disease that, in the opinion of the Investigator, precludes further study drug treatment
- Subject decision: a subject may withdraw consent to participate in the study at any time

Study centers that deviate significantly from the protocol without prior approval from the Sponsor and regulatory authorities may be discontinued from the study. The Investigator at each study center is responsible for ensuring the accuracy and completeness of all research records, the accountability of study drug, and the conduct of clinical and laboratory evaluations as outlined in the protocol.

All subjects are required to adhere to the protocol-specified visit schedule. If a subject misses a scheduled visit, attempts should be made to reschedule the visit within the visit windows described above. Failure to attend scheduled study visits may result in discontinuation from the study.

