5.1.1 Presentation of results

The following statistics will be presented:

- For quantitative variables: number of available data, number of missing values, mean, standard deviation, median, Q1, Q3, minimum and maximum values. When relevant, confidence intervals will be calculated for the mean (Student CI) or the median (Hahn & Meeker 1991).
- For qualitative variables: number of available data, number of missing values number and percentage of observations in each category of the variable. Except if otherwise specified, percentages will be calculated using the number of available data as denominator (i.e., not including missing values). When relevant, confidence intervals of proportions will be calculated using the Clopper-Pearson method (Clopper & Pearson 1934).

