5.2.2 Patient disposition and study discontinuations

Patient disposition will be described using a table (Statistical table 14.1.19) and a flow chart (Figure 14.1). The following variables will be tabulated :

- Number of randomised patients, total and per treatment group
- Number of randomised patient by visit, total and per treatment group
- Number of randomised patients who completed the study treatment as planned (until the 7th cycle on week 24), total and by treatment group
- Number of randomised patients who prematurely discontinued the study treatment (before the 7th cycle on week 24), total and by treatment group
- Number of randomised patients who prematurely discontinued the study treatment before completing the first three cycles and/or who do not have at least one post-cycle 3 evaluation of the primary efficacy criterion (FVC [% predicted])
- Number of randomised patients withdrawn from the study (before week 28) total and by treatment group

The numbers of patient within each dataset (ATS, PP and SAF), globally and by treatment group, will be provided (Statistical table 14.1.20, Listing 16.2.3.1) along with reasons for exclusion from the ATS and PP populations (Statistical table 14.1.21 and 14.1.22 respectively). Reasons for exclusions from the ATS and PP populations will also be provided in Listing 16.2.3.2, according to ICHE3.

A breakdown of the reasons for study discontinuations (Statistical Table 14.1.23 will be tabulated by treatment group. All reasons for study discontinuations will be provided in Listing 16.2.1.

All protocol deviations classified during the blinded review meeting according to definitions provided in section 3.1.1 (Major deviations) and 3.1.2 (Minor deviations) will be tabulated by treatment group for the ATS (Statistical table 14.1.24 and 14.1.25 respectively). All major and minor protocol deviations will also be provided in Listing 16.2.2, according to ICHE3.

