5.3.2 Handling of Dropouts or Missing Data

Missing data in efficacy analysis:

The statistical model (linear mixed models for repeated measures) used for the primary and most secondary efficacy analyses will be used without imputation of missing values and are valid under the assumption of missingness at random.

Multiple imputation techniques will be used for the sensitivity analysis on the initially planned primary analysis (see Section 5.2.5.1).

All available efficacy and safety data will be included in data listings and tabulations.

Missing or incomplete dates:

For all listings, missing or incomplete dates will be left as they were recorded.

For calculation / sorting / assignment based on dates (*e.g.*, treatment emergent AEs, concomitant medications...), the following rules will apply:

- The most conservative approach will be considered (*i.e.*, if the onset date of an AE/concomitant medication is missing / incomplete, it will be assumed to have occurred during the study treatment phase (*i.e.*, a TEAE for AEs) except when the partial onset date or other available data indicates differently (*e.g.*, start date day missing, but month before the month of baseline date, or stop date before baseline date).
- Medical history or disease diagnosis with missing/incomplete date will be assumed to have occurred before any study treatment except when the partial onset date or other available data indicates differently.
- Assignations based on dates will be reviewed and confirmed or infirmed during the data review meeting
- Missing or partial start or end dates of IMP administration, if any, will be reviewed during the data review meeting.

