5.4.4 Visit windowing

The agreement between realized visit date and the expected visit time frame will be reviewed during blind review meeting.

For premature discontinued patient, all data collected during the End of Study visit will be reallocated to the visit following last infusion.

6 Modifications from the statistical sections in the protocol

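### SO6: stable FVC is defined on a signed change, so any loss counts as stable; separately, patients who die or are withdrawn for progression drop out of the responder comparisons

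*SAP*

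**What the plan says.** **Definition of stable.** SAP 4.1.2 and SO6 in SAP 5.2.5.2 list "Subjects with stable disease by FVC [% predicted], defined as a change in FVC [% predicted] of" less than 5%, and a companion endpoint with a change below 100 ml. Protocol 3.2 uses the same form. None of these places mentions an absolute value. SAP section 8 defines change from baseline as the visit value minus the baseline value and adds that negative values are decreases. It defines percent change separately.

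**Data used.** SAP 5.2.5.2 states: "For all secondary efficacy endpoints, the analyses will be based on observed data only". SAP 5.1.1 adds that, unless otherwise specified, "percentages will be calculated using the number of available data as denominator". The arms are compared by odds ratio with 90% CI and an exact Cochran-Mantel-Haenszel test adjusted for stratum, on the All Treated Set (ATS) and the per-protocol (PP) set.

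**Patients who stop early.** Protocol 5.4 places the End of Study visit 4 weeks after the last dose. For these patients, SAP 5.4.4 says that "all data collected during the End of Study visit will be reallocated to the visit following last infusion". Protocol 5.2 lists progression among the reasons for withdrawal from the study, and "The reason for study withdrawal is to be documented in the" source documents and the eCRF. SAP 3.1.3 lists "Progression of disease that, in the opinion of the Investigator, precludes further study drug treatment", but as a reason to stop study drug.

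**Related provisions.** SAP 5.3.2 ties the missing-at-random argument to the linear mixed models and says: "Multiple imputation techniques will be used for the sensitivity analysis on the initially planned primary analysis". SAP 5.2.2 plans this by arm: "A breakdown of the reasons for study discontinuations". Deaths are tabulated under safety (SAP 5.2.6.1). SAP 5.1 excepts selected secondary endpoints from the observed-data rule and points to 5.2.5.2 for details.

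**The concern.** The stable rule does not do what its name says. A patient who loses 15 points has a signed change of -15, which is below 5, and so is counted as stable. The same patient is also a decliner at both thresholds. An arm with more losses then looks more stable.

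The second issue concerns bad outcomes that are never scored. A patient who dies, or who leaves the study because the disease has progressed, and who has no Week 28 FVC is in neither the numerator nor the denominator of an endpoint called decline. Nothing planned for SO6 shows what difference that makes.

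**Working it through.** **Inputs (SAP 2.3.2).** Change is normal with SD 5. The mean is 0.75 on PRM-151 (the plan says at least 0.75). On placebo it is -1.5 with background therapy (75%) and -3 without (25%). There are 68 and 34 evaluable patients, 78 and 39 enrolled, and alpha is 0.10 two-sided.

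**The plan's own figure.** The difference is 0.75 - (0.75 × -1.5 + 0.25 × -3) = 2.625. Placebo n = 1.5 × 25 × (1.645 + 0.842)² / 2.625² ≈ 33.7, so 34 + 68 = 102, as stated. Power is 80.4% (normal) or 79.9% (t). No power is stated for SO6.

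**Stable, 5-point cut-off**

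- PRM-151: P(change ≤ -5) = Φ(-1.15) = 0.1251; P(change ≥ 5) = 1 - Φ(0.85) = 0.1977.
- Placebo: P(change ≤ -5) = 0.75 Φ(-0.7) + 0.25 Φ(-0.4) = 0.2676; P(change ≥ 5) = 0.75 [1 - Φ(1.3)] + 0.25 [1 - Φ(1.6)] = 0.0863.

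| Reading | Formula | PRM-151 | Placebo | Odds ratio |
|---|---|---|---|---|
| Signed, as written | 1 - P(increase ≥ 5) | 80.2% | 91.4% | 0.38 |
| Absolute | 1 - P(increase ≥ 5) - P(decline ≥ 5) | 67.7% | 64.6% | 1.15 |

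The signed result is the reciprocal of the odds ratio for an increase of at least 5 points (2.61; 1/2.61 = 0.38), so the endpoint adds no information. The same logic applies at 100 ml. The plan gives no assumptions in ml, so that version is not quantified.

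**Who leaves the SO6 comparison.** With the End of Study visit 4 weeks after the last dose and its data moved to the visit after the last infusion, that FVC becomes a Week 28 value only if the last infusion was at Week 24. Otherwise the patient has no Week 28 value and drops out under the observed-data rule.

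**Illustration, decline of at least 5 points.** The number of patients is an assumption (3 or 6); the documents give none.

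- Observed data: 12.5% v 26.8%, odds ratio 0.39. The expected counts are 8.5 of 68 and 9.1 of 34, giving an approximate 90% CI of 0.16 to 0.94.
- With k patients in an arm of N counted as decliners, the rate is [k + (N - k)p]/N, with N = 78 and 39.
- Three patients split 2:1: 14.75% v 28.64%, odds ratio 0.43.
- Six split 4:2: 16.99% v 30.52%, odds ratio 0.47.
- All six on placebo: 0.23. All six on PRM-151: 0.65.

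Each value lies inside the observed-data interval. That interval treats all 68 and 34 as having an observed Week 28 FVC. Under the protocol's original last-observation-carried-forward rule, some evaluable patients might not have one. With 54 and 27 observed (an assumption), it widens to 0.15 to 1.05.

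**Decline of at least 10 points.** The expected counts are 1.1 and 1.8. The chance that at least one arm has no decliner is 1 - (1 - 0.9842^68)(1 - 0.9464^34) ≈ 0.44, in which case the odds ratio is zero, infinite or undefined. No useful sensitivity figure can be given.

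**Relative reading of 5%.** Over the eligible baseline range, 5% of 50 is 2.5 points and 5% of 90 is 4.5 points. If the change distribution is the same at every baseline, the decline rates are 25.8% v 45.1% (odds ratio 0.42) and 14.7% v 30.1% (0.40), against 12.5% v 26.8% (0.39) for 5 points.

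**The case against.** Both documents declare observed-data analysis for secondary endpoints, and SAP 5.1.2 warns that the tests are unadjusted for multiplicity. SO6 concerns pulmonary function; mortality-related events have their own objective (SO5). Deaths, respiratory decline, acute exacerbations and discontinuation reasons are all reported, and the SO6 tables will show the number missing. The primary mixed model uses the earlier FVC values of patients who drop out. Eligibility requires a life expectancy of at least 9 months, so deaths by Week 28 may be few. All of this stands, and it is why the second point is a suggestion. None of it changes the SO6 odds ratios.

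The composite also has weaknesses that stand. Protocol 1.1 attributes about 60% of deaths in IPF to the disease itself, yet every death would count as an FVC decline. A patient withdrawn for progression would be scored as a decliner even if the last measured FVC was stable. Worsening coded as an adverse event or subject decision stays excluded. The PP set is not free of the problem either: it requires a post-cycle 3 FVC, so later deaths and withdrawals remain in PP and drop out of its SO6 tables in the same way.

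On the percentage cut-offs, SAP section 8 separates change from percent change, and the protocol's Phase 1 summary says relative when it means relative. That point is close to settled already. The objection does not reach the stable definition beyond calling it editorial, and a rule that reverses the apparent effect when followed literally is more than that.

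A reader might infer that SO6 is biased in favour of PRM-151, or that deaths are concealed. The documents support neither: they give no counts by arm, the illustration moves both ways, and deaths are tabulated. Nor can the plan's 15% non-evaluability be used as a bound on these patients, because it covers every reason for loss and was set when carried-forward values counted as evaluable.

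**Conclusion.** The stable definition is wrong as written. Combined with the signed change of SAP section 8, it makes the endpoint the mirror image of the increase endpoint. On the plan's assumptions (normal changes, SD 5, the stated means and 75/25 mix) the odds ratio is 0.38 instead of 1.15. A programmer may well assume absolute values, since stable naturally lies between decline and increase, but the text does not say so.

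The handling of death and progression without a Week 28 FVC is a gap in supportive analysis and not an error. Its size depends on a number that the documents do not give, and its direction is unknown. At 5 points, 3 to 6 assumed patients move the odds ratio modestly relative to its interval; at 10 points the data are too sparse to say anything useful. The percentage-point wording and the conflict between SAP 5.1 and 5.2.5.2 on imputation are editorial only. The primary test and the sample size are not affected.

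**What to change.** Before unblinding:

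1. In SAP 4.1.2 and SO6, define stable as |change| < 5 percentage points and |change| < 100 ml.
2. Keep the observed-data SO6 analysis as the main one. Add one pre-specified supportive analysis on the ATS with the same exact stratified test:
   - An observed Week 28 FVC, including one assigned to Week 28 under SAP 5.4.4, takes precedence.
   - Without one, death before Week 28, or study withdrawal with progression as the recorded reason, counts as decline at every threshold, as not stable and as not increased. Use the study discontinuation reason (Protocol 5.2, SAP 5.2.2); stopping study drug alone (SAP 3.1.3) does not qualify.
   - Other missing values stay excluded.
   - The same table shows, per arm, the number without a Week 28 FVC by reason.
3. State that the 5% and 10% cut-offs are percentage points. In SAP 5.1, delete the exception for selected secondary endpoints or name them, so that it agrees with 5.2.5.2.

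The cost is one extra table set and a few wording edits, with no new data and no imputation. The supportive result mixes FVC with all-cause death and investigator-judged progression, so it belongs beside the observed-data result and does not replace it.

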2.2.2 Secondary objectives (SO)

The secondary objectives of this study are:

- **SO1:** To determine the effect size of PRM-151 relative to placebo in change from Baseline to Week 28 in normal lung parenchyma as quantified on high-resolution CT (HRCT) imaging analysis, pooling subjects on a stable dose of pirfenidone or nintedanib with subjects not on other treatment for IPF.
- **SO2:** To determine the effect size of PRM-151 relative to placebo in change from Baseline to Week 28 in mean FVC [% predicted], separately in subjects on a stable dose of pirfenidone or nintedanib and in subjects not on other treatments for IPF.
- **SO3:** To determine the effect size of PRM-151 relative to placebo in change from Baseline to Week 28 in normal lung parenchyma as quantified on HRCT imaging analysis, separately in subjects on a stable dose of pirfenidone or nintedanib and in subjects not on other treatments for IPF.
- **SO4:** To assess the tolerability and safety of PRM-151 in subjects with IPF through Week 28.
- **SO5:** To assess the ability of PRM-151 to reduce disease-related events associated with mortality

- **SO6:** To determine the effect size of PRM-151 relative to placebo on pulmonary function in addition to mean change in FVC [% predicted]
- **SO7:** To determine the effect size of PRM-151 relative to placebo on 6 minute walk distance
- **SO8:** To determine the effect size of PRM-151 relative to placebo on DLCO.

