2.3.2 Determination of sample size

The primary objective is not to formally demonstrate the superiority of PRM-151 over placebo, but to provide a reliable estimate of the size of the effect of PRM-151 on absolute change from baseline to 28 weeks in mean FVC [% predicted], hereafter referred to as the primary endpoint. Nevertheless, the sample-size has been calculated to ensure a sufficient power to demonstrate the efficacy of PRM-151 over placebo on the primary endpoint under a set of hypotheses on effect sizes in the two groups and on the variability of the primary endpoint. The primary endpoint will be tested in a model with two types of subjects: subjects on a stable dose of pirfenidone or nintedanib, and subjects not on other treatment for IPF. The sample size calculation is based on the following assumptions:

- Primary endpoint is normally distributed.
- Homogeneity of variance, *i.e.*, the standard deviation is the same in both arms, and for both types of subjects.
- Randomization ratio PRM-151: placebo equals 2:1.
- Expected value of the primary endpoint for subjects on pirfenidone or nintedanib will be -1.5%.
- Expected value of the primary endpoint for subjects on no other treatment will be -3%.
- Expected value of the primary endpoint for subjects on PRM-151 will be $\geq 0.75\%$.
- Standard deviation of the primary endpoint is 5%.
- 75% of subjects will be on a stable dose of pirfenidone or nintedanib.
- 25% of subjects will not be on other treatment for IPF.
- Significance level (α)=0.10 two-sided.
- Desired power to demonstrate superiority is 80%.

A sample size of one hundred and two (102) evaluable subjects in total (68 PRM-151 and 34 placebo) is enough to demonstrate statistical significance at $p < 0.10$ two-sided with a power of 80% under the above assumptions. Assuming a non-evaluability rate of about 15%, 117 subjects in total (78 PRM-151 and 39 placebo) are to be enrolled. Stratified randomization will ensure a balance of PRM-151: placebo within patients on pirfenidone or nintedanib and not on any other therapy, with at least 25% of patients on no other therapy.

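### For the FVC responder endpoints in SO6 the odds ratio is the only between-arm measure named, and at the 10% thresholds it will often be zero, infinite or undefined

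*SAP*

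**What the plan says.** SO6 is framed as an effect-size objective in SAP 2.2.2: "To determine the effect size of PRM-151 relative to placebo on pulmonary function in addition to mean change in FVC [% predicted". SAP 5.2.5.2 carries it out on ten binary endpoints: decline and increase in FVC % predicted at 5% and 10%, decline and increase in FVC at 100 ml and 200 ml, and stable disease on each scale.

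For these it plans descriptive statistics and odds ratios (PRM-151 over placebo) "with their 90% CIs will be calculated by treatment group and stratification level for" the listed endpoints. The groups are then compared with a Cochran-Mantel-Haenszel test adjusted for stratum, and the section adds: "Due to the small sample-size, the exact version of the test will be used. Odds ratio (with 90% CI) together with p-values will be reported".

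Three other places bear on this. SAP 5.1.1 defines the descriptive statistics for qualitative variables as counts and percentages, with Clopper-Pearson intervals when relevant. SAP 9.1 lists a common odds ratio table for SO6 (14.2.9.1.b to 14.2.9.2.b) and a companion treatment-effect table whose content is not defined. SAP 5.2.5.2 restricts all secondary analyses to observed data. The common-odds-ratio estimator, the interval method and the handling of empty cells are not stated anywhere.

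**The concern.** The SAP recognises small numbers when it chooses the test, but not when it chooses the estimate. An odds ratio is zero or infinite when one arm has no responder and undefined when neither arm has one. A standard large-sample interval cannot be computed in either case. Changes of 10 points in FVC % predicted should be rare under the planning assumptions, and the strata are small.

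If the odds ratio fails, the SO6 tables for those endpoints contain a p-value and two percentages but no usable effect relative to placebo, which is what the objective asks for. Separately, an interval whose method is left to programming may not agree with the exact p-value printed beside it.

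**Working it through.** **Inputs (SAP 2.3.2).** Placebo means: "Expected value of the primary endpoint for subjects on pirfenidone or nintedanib will be -1.5" and "Expected value of the primary endpoint for subjects on no other treatment will be -3". PRM-151: "Expected value of the primary endpoint for subjects on PRM-151 will be" at least 0.75; 0.75 is used here in both strata. Normal distribution, common SD 5, 2:1 allocation, strata 75/25, alpha "0.10 two-sided", "Desired power to demonstrate superiority is 80"%.

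**The plan's own figure.** Mean difference = 0.75 × (0.75 + 1.5) + 0.25 × (0.75 + 3) = 2.625. Placebo n = 1.5 × (1.645 + 0.842)² × 25 / 2.625² ≈ 33.7, so 34. Total = 3 × 34 = 102, as stated. The SAP gives no responder rates, so they are derived from this model.

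**Step 1: responder rates.** With x the threshold in points, the rate of an increase is 1 − Φ((x − mean)/5) and of a decline 1 − Φ((x + mean)/5). For example, an increase of at least 10 on PRM-151 is 1 − Φ(1.85) = 3.2%.

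| Endpoint | PRM-151 | Placebo, background | Placebo, none | Expected responders (68 vs 34) |
|---|---|---|---|---|
| Increase ≥10 | 3.2% | 1.1% | 0.5% | 2.2 vs 0.3 |
| Decline ≥10 | 1.6% | 4.5% | 8.1% | 1.1 vs 1.8 |
| Increase ≥5 | 19.8% | 9.7% | 5.5% | 13.4 vs 3.0 |
| Decline ≥5 | 12.5% | 24.2% | 34.5% | 8.5 vs 9.0 |

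**Step 2: chance that the odds ratio fails.** Stratum sizes are taken as 51 vs 26 (background) and 17 vs 8 (none). An arm of n subjects has no responder with probability (1 − p)ⁿ. The odds ratio fails with probability 1 − (1 − A)(1 − B), where A and B are those probabilities for the two arms. Arms made up entirely of responders add nothing visible at these rates. The pooled Mantel-Haenszel odds ratio fails when an arm is empty across both strata.

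- Increase ≥10, background: A = 0.9678⁵¹ = 0.189, B = 0.9893²⁶ = 0.756, so 1 − 0.811 × 0.244 = 0.80.
- Increase ≥10, none: A = 0.574, B = 0.963, so 0.98. Neither arm has a responder in 0.574 × 0.963 = 55% of trials.
- Decline ≥10, none: A = 0.763, B = 0.510, so 0.88.

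| Endpoint | Background | None | Pooled |
|---|---|---|---|
| Increase ≥10 | 80% | 98% | 76% |
| Decline ≥10 | 61% | 88% | 44% |
| Increase ≥5 | 7% | 65% | 4.5% |
| Decline ≥5 | 0.2% | 13% | <0.1% |
| Stable (<5) | 0% | 2% | <0.1% |

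**Step 3: sensitivity.** Pooled failure over SD 4 to SD 6: increase ≥10, 97% to 44%; decline ≥10, 88% to 12%. With no treatment effect at SD 5: 87% and 18%. With all 117 enrolled subjects evaluable: 72% and 37% pooled; by stratum (background/none) 77%/98% and 55%/85%.

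**Step 4: ml endpoints.** These need an assumed conversion. The baselines in protocol Table 1-1 give 2.2 l/63 ≈ 35 ml and 2.9 l/79 ≈ 37 ml per point. The pooled odds ratio then fails in at most 10% of trials (increase ≥200 ml) and almost never for the other four. In the no-therapy stratum it fails in 70–73% for increase ≥200 ml and 34–36% for increase ≥100 ml.

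**Step 5: agreement of interval and p-value.** Take responders of 2/51 and 1/17 on PRM-151 against 3/26 and 2/8 on placebo. The large-sample Mantel-Haenszel 90% CI is 0.07 to 0.92, which excludes 1, while the exact stratified p is 0.113. In simulation under the planning model, that interval and the exact test disagree at the 0.10 level in about 5% of trials for increase ≥5 and 4% for decline ≥5.

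**The case against.** Several points on the other side stand.

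- A reader might infer that SO6 reports odds ratios and nothing else. It does not: counts and percentages by arm and stratum are planned and remain defined with empty cells. They describe each arm, however, and are not an effect relative to placebo.
- A reader might infer that the exact p-value has no matching interval. The SAP does not say so; it leaves the method unnamed. An exact conditional interval would be consistent with an exact test, and it exists even when one arm is empty. With 2/51 and 0/17 against 0/26 and 0/8 it runs from 0.15 to infinity. It is then informative on one side only, and with no responders in either arm there is none.
- A reader might infer that SO6 as a whole cannot deliver an effect size. That is too broad. Eight of the ten pooled odds ratios are estimable in about 90% of trials or more, the pooled odds ratio for decline ≥10% is finite in 56%, and lung function is also analysed on continuous scales (SO8 for DLCO, EO1 for FVC in ml).
- The failure rates come from normal tails and move a great deal with the SD.
- These are secondary analyses without multiplicity control, and SAP 5.1.2 already asks for cautious reading.

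What remains is that the stratum odds ratios the SAP plans will mostly fail at both 10% thresholds, and nothing in the plan takes their place as a comparison with placebo.

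**Conclusion.** The point holds in a limited form. At SD 5 and 102 evaluable subjects, stratum odds ratios fail in 61% to 98% of trials for the two 10% endpoints and in about 65% for increase ≥5% in the no-therapy stratum. The pooled odds ratio usually fails for increase ≥10% (76%) and fails in a substantial minority of trials for decline ≥10% (44%). The possible disagreement between interval and p-value is a modest risk arising from an unnamed method, not a demonstrated contradiction.

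This rests on the normal planning model, on PRM-151 at its stated lower bound of 0.75, on stratum sizes rounded to whole subjects, and on reading the thresholds as absolute points of FVC % predicted, in line with the definition of change in SAP section 8. The primary analysis and the trial's main conclusion are not affected. The change is worth making because it is cheap and gives SO6 a finite effect size for every endpoint.

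**What to change.** In SAP 5.2.5.2 (SO6):

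1. For every responder endpoint, add the stratum-weighted difference in proportions (PRM-151 minus placebo) with a 90% CI that stays defined with empty cells, and name the method, for example a stratified Newcombe or Miettinen-Nurminen score interval. Show the risk difference beside the counts within each stratum.
2. State that the common odds ratio takes its 90% CI from the exact conditional method that corresponds to the exact test.
3. Keep the stratum odds ratios, and print them as not estimable where a cell is empty.

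The cost is some SAP wording and one extra column in the 14.2.9 tables, settled before unblinding. The exact odds-ratio interval will be somewhat wider than a large-sample one. The risk-difference interval may occasionally differ from the exact p-value, so the SAP should say that the p-value belongs to the exact test. Sample size, design and conduct do not change.
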